## 4. STUDY DESIGN

### 4.1. Overall design

The study design diagram is provided in Section 1.2.

**Experimental design:** Phase 3, randomized, controlled, partial blind study.

**Study groups and vaccination visits:**

The study will aim to enroll approximately 2600 participants, i.e., 1800 participants in China [2:1 randomization allocation between RSV OA group (China) and Placebo group (China)], 800 participants in RSV OA group (Overseas).

Study participants in China will be randomly assigned to the RSV OA group (China) or to the Placebo group (China) (2:1) to receive 1 single dose of investigational RSVPreF3 OA vaccine or Placebo, respectively on Visit 1 (Day 1).

The participants in the RSV OA vaccine overseas group will receive 1 single dose of investigational RSVPreF3 OA vaccine on Visit 1 (Day 1).

**Duration of study:** The total duration of the study per participant will be approximately 7 months.

**Sampling schedule:**

For the study participants in RSV OA Vaccine group (Overseas), a blood sample of approximately 15 mL will be collected at screening visit to test for HIV, HBV, HCV and Syphilis.

Three blood samples (approximately 10 mL each) will be collected from all participants to evaluate the immune response to the investigational RSVPreF3 OA vaccine on Day 1 (pre-vaccination), Day 31 (post vaccination) and Month 6.

**Primary completion date (PCD):** The PCD will be when the last participant completes Day 31, as per SoA (Section 1.3).

**Blinding:** Partially blind. Refer to Section 6.4 for details.

**Safety monitoring:** GSK's Safety Review Team (SRT) will oversee the safety of the study participants and study conduct (refer to Section 8.3.3).

**ARI surveillance:** Surveillance for ARI detection will be carried out during the entire study in participants in China, via spontaneous reporting by the participant (starting on the vaccination day [Visit 1]) and via scheduled China site staff contacts (starting from Visit 2 onwards). These contacts will be every 2 weeks during the RSV season and every month during the inter-season periods. For detailed information on activities involved in ARI surveillance, refer to Table 2.

**Data collection:** Standardized Electronic Case Report Form (eCRF) will be used. Solicited and unsolicited adverse events will be collected using paper diaries.

**End of study (EoS):** Refer to Section 4.4 for details.

The description of the vaccine(s)/product is presented in Table 9.

## 4.2. Scientific rationale for study design

RSV is associated with serious illness in older adults and high-risk adults globally and in China. The efficacy of a single dose of the RSVPreF3 OA investigational vaccine in the prevention of RSV-LRTD caused by RSV A and/or RSV B in older adults  $\geq 60$  YOA has been demonstrated in the global Phase 3 clinical study RSV OA=ADJ-006 (refer to IB). The current study is designed as a Phase 3, partially blind, controlled study to demonstrate the NI of the immune response of RSVPreF3 OA investigational vaccine in older adults in China, compared to older adults in the same age range to be enrolled from overseas countries that participated in the RSV OA=ADJ-006 study. Safety will also be evaluated in all study groups.

The inclusion of a group of participants overseas will allow direct and parallel bridging and comparison for immunogenicity between different populations (China vs Overseas), which is in line with the requirements in draft local guidelines on immunogenicity bridging clinical trial for prophylactic vaccines issued by CDE [CDE, 2022].

Immune protection against RSV in older people is incompletely understood and probably multifactorial. Older adults with low titers of serum NAb have been reported to be at greater risk of developing symptomatic RSV infection and of hospitalization than those who have high antibody titres [Falsey, 1998; Walsh, 2004]. The immunogenicity endpoints in this study will therefore be relying on virus neutralization assays against RSV-A and RSV-B subtypes.

Occurrence of RSV-associated ARI and LRTD will also be monitored in all participants in China during the study.

### 4.2.1. Case definitions

All study participants in China reporting at least 2 ARI symptoms/signs meeting the ARI case definition (see Table 8) will be followed up for ARI assessment. Diagnosis and treatment of each ARI should be performed according to the local standard of care. RT-PCR testing for RSV will be performed at GSK and GSK-designated laboratory. Therefore, all study participants in China with ARI will be requested to follow all study procedures and study contacts defined for the ARI surveillance (i.e., reporting of ARI symptoms/signs, ARI visit and follow-up contacts, etc).

**Table 8 Case definitions for ARI and LRTD**

Endpoint	Case definition																						
ARI (Trigger for swabbing)	
Presence of:
 
 
at least 2 respiratory symptoms/signs for at least 24 hours
 
 
OR
 
 
at least 1 respiratory symptom/sign + 1 systemic symptom/sign for at least 24 hours
 
 
  
 Respiratory symptoms and signs	Systemic symptoms and signs	
   
 - Nasal congestion/rhinorrhea	- Temperature <math>\geq 38.0^{\circ}\text{C}</math> /feverishness	
 
 - Sore throat	- Fatigue	
 
 - New or increased sputum	- Body aches	
 
 - New or increased cough	- Headache	
 
 - New or increased dyspnea (shortness of breath)	- Decreased appetite	
 
 - New or increased wheezing		
 
 - New or increased crackles/ronchi based on chest auscultation		
 
 - Respiratory rate <math>\geq 20</math> respirations/min		
 
 - Low or decreased oxygen saturation (= O2 saturation <95% or <math>\leq 90\%</math> if pre-season baseline is <95%)		
 
 - Need for oxygen supplementation		
  
	Respiratory symptoms and signs	Systemic symptoms and signs	- Nasal congestion/rhinorrhea	- Temperature $\geq 38.0^{\circ}\text{C}$ /feverishness 	- Sore throat	- Fatigue	- New or increased sputum	- Body aches	- New or increased cough	- Headache	- New or increased dyspnea (shortness of breath)	- Decreased appetite	- New or increased wheezing 		- New or increased crackles/ronchi  based on chest auscultation		- Respiratory rate $\geq 20$ respirations/min 		- Low or decreased oxygen saturation (= O 2 saturation <95% or $\leq 90\%$ if pre-season baseline is <95%) 		- Need for oxygen supplementation 	
Respiratory symptoms and signs	Systemic symptoms and signs																						
- Nasal congestion/rhinorrhea	- Temperature $\geq 38.0^{\circ}\text{C}$ /feverishness 																						
- Sore throat	- Fatigue																						
- New or increased sputum	- Body aches																						
- New or increased cough	- Headache																						
- New or increased dyspnea (shortness of breath)	- Decreased appetite																						
- New or increased wheezing 																							
- New or increased crackles/ronchi  based on chest auscultation																							
- Respiratory rate $\geq 20$ respirations/min 																							
- Low or decreased oxygen saturation (= O 2 saturation <95% or $\leq 90\%$ if pre-season baseline is <95%) 																							
- Need for oxygen supplementation 																							
RT-PCR-confirmed RSV-ARI 	An event meeting the case definition of ARI with at least one RSV-positive swab detected by RT-PCR. 																						
LRTD	
Presence of:
 
 
at least 2 lower respiratory symptoms/signs for at least 24 hours including at least 1 lower respiratory SIGN
 
 
OR
 
 
at least 3 lower respiratory symptoms for at least 24 hours
 
 
  
 Lower respiratory symptoms	Lower respiratory signs	
   
 - New or increased sputum	- New or increased wheezing	
 
 - New or increased cough	- New or increased crackles/ronchi based on chest auscultation	
 
 - New or increased dyspnea (shortness of breath)	- Respiratory rate <math>\geq 20</math> respirations/min	
 
 	- Low or decreased oxygen saturation (= O2 saturation <95% or <math>\leq 90\%</math> if pre-season baseline is <95%)	
 
 	- Need for oxygen supplementation	
  
	Lower respiratory symptoms	Lower respiratory signs	- New or increased sputum	- New or increased wheezing 	- New or increased cough	- New or increased crackles/ronchi  based on chest auscultation	- New or increased dyspnea (shortness of breath)	- Respiratory rate $\geq 20$ respirations/min 		- Low or decreased oxygen saturation (= O 2 saturation <95% or $\leq 90\%$ if pre-season baseline is <95%) 		- Need for oxygen supplementation 										
Lower respiratory symptoms	Lower respiratory signs																						
- New or increased sputum	- New or increased wheezing 																						
- New or increased cough	- New or increased crackles/ronchi  based on chest auscultation																						
- New or increased dyspnea (shortness of breath)	- Respiratory rate $\geq 20$ respirations/min 																						
	- Low or decreased oxygen saturation (= O 2 saturation <95% or $\leq 90\%$ if pre-season baseline is <95%) 																						
	- Need for oxygen supplementation 																						
RT-PCR-confirmed RSV-LRTD 	An event meeting the case definition of LRTD with at least one RSV-positive swab detected by RT-PCR. 																						
RT-PCR-confirmed severe RSV-LRTD – Definition 1 “Clinical symptomology” 	
Presence of a LRTD with the following criteria:
 
 
at least 2 lower respiratory SIGNS
 
 
AND
 
 
with at least one RSV-positive swab detected by RT-PCR
 
 
Lower respiratory signs
 
 
- New or increased wheezing
 
- New or increased crackles/ronchi based on chest auscultation
 
- Respiratory rate <math>\geq 20</math> respirations/min
 
- Low or decreased oxygen saturation (= O2 saturation <95% or <math>\leq 90\%</math> if pre-season baseline is <95%)
 
- Need for oxygen supplementation
 
																						

Endpoint	Case definition
RT-PCR-confirmed severe RSV-LRTD – Definition 2 “Supportive therapy” 	Presence of a LRTD with at least one of the following criteria  : 
 
• Need for oxygen supplementation
 
• Need for positive airway pressure therapy (e.g. CPAP)
 
• Need for other types of mechanical ventilation
 
 AND 
 
• with at least one RSV-positive swab detected by RT-PCR
 

ARI: acute respiratory illness; CPCA: continuous positive airway pressure; LRTD: lower respiratory tract disease; RSV: respiratory syncytial virus; RT-PCR: reverse transcription polymerase chain reaction.

1. Feverishness is defined as the feeling of having fever without objective measurement.
2. Reported by study participant or investigator.
3. Reported by investigator.
4. Throat and/or nasal swab samples collected at ARI visits for RT-PCR testing will be collected within 6 days after ARI onset (i.e., up to Day 7).
5. Refer to Section 8.2 for details on the counting of cases that are positive for RSV.
6. In case the participant was already receiving any of these for treating/controlling any pre-existing condition, any significant change or adaptation in the used therapy should be taken into account.

#### 4.2.2. Rationale for the use of placebo

As there is currently no licensed RSV vaccine available in China, a Placebo group (receiving saline solution) will be used as control for safety/reactogenicity assessments.

Participants who received the placebo during the study may be provided with GSK RSVPreF3 OA vaccine after the study is completed and the RSVPreF3 OA vaccine is launched in China, depending on study results, local standards and regulations. Study site will contact the participants when this can be provided.

#### 4.2.3. Rationale for study blinding

Given the difference in reconstitution and visual appearance of the RSVPreF3 OA investigational vaccine and the saline solution used as placebo, double blinding is not possible, and the study will be conducted in an observer-blind manner for participants in RSV OA group (China) and Placebo group (China). Please refer to [Definition of Terms](#) for the definition of observer blind. Participants enrolled in the RSV OA group (Overseas) will be aware of the intervention they receive, however the sample testing for immunogenicity will be blinded.

Further information on blinding and unblinding is provided in Section 6.4.

#### 4.3. Justification for dose

A single dose (0.5 mL) of the licensed formulation (120 µg RSVPreF3/AS01E) will be used in this study.

#### 4.4. End-of-study definition

A participant is considered to have completed the study if the participant has completed all periods of the study including the last scheduled procedure shown in the SoA (Section 1.3).

LSLV (Month 6 for overseas participants; Visit3 [Month 6] or last ARI visit/ contact whichever is later for study participants in China) or Date of the last testing/reading released of the Human Biological Samples or imaging data, related to primary and secondary endpoints, whichever occurs later. EoS must be achieved no later than 8 months after LSLV. EoS cannot be before LSLV.

## 5. STUDY POPULATION

Prospective approval of protocol deviations to recruitment and enrollment criteria, also known as protocol waivers or exemptions, is not permitted.

### 5.1. Inclusion criteria

All participants must satisfy ALL the following criteria at study entry:

- Adult male or female of  $\geq 60$  YOA at the time of study intervention administration, who live in the community dwelling (CD participants) (see definition of terms for the definition). INC#1
- Participants who, in the opinion of the investigator, can and will comply with the requirements of the protocol (e.g., completion of the diary cards, attend regular phone calls/study site visits, perform self-swabbing (study participants in China only), ability to access and utilize a phone or other electronic communications). INC#2

*Note: In case of physical incapacity that would preclude the self-completion of the diary cards, either site staff can assist the participant (for activities performed during site visits) or the participant may assign a caregiver to assist him/her with this activity (for activities performed at home). However, at no time, the site staff or caregiver will evaluate the participant's health status while answering diaries or make decisions on behalf of the participant.*

- Participants who are medically stable in the opinion of the investigator at the time of vaccination. Participants with chronic stable medical conditions with or without specific treatment, such as diabetes, hypertension or cardiac disease, are allowed to participate in this study if considered by the investigator as medically stable. INC#3
- Written or witnessed informed consent obtained from the participant (participant must be able to understand the informed consent) prior to performance of any study specific procedure. INC#4

### 5.2. Exclusion criteria

Participants are excluded from the study if any of the following criteria apply:

#### 5.2.1. Medical Conditions

- History of any reaction or hypersensitivity likely to be exacerbated by any component of the study intervention(s) (For details on components of study intervention administered, refer to [Table 9](#) and *Arexvy* [[Summary of Product Characteristics](#), 2023; [Prescribing Information](#), 2023]. EXC#1

- Any clinical conditions for which serum samples would be prohibited for transfer to local central lab for testing. These clinical conditions include hepatitis B, hepatitis C, HIV and Syphilis based on medical history and physical examination (all participants) and laboratory screening tests (overseas participants). EXC#2
- Any confirmed or suspected immunosuppressive or immunodeficient condition resulting from disease (e.g., current malignancy, human immunodeficiency virus) or immunosuppressive/cytotoxic therapy (e.g., medication used during cancer chemotherapy, organ transplantation, or to treat autoimmune disorders), based on medical history and physical examination (no laboratory testing required). EXC#3
- Any history of dementia or any medical condition that moderately or severely impairs cognition. EXC#4
- Recurrent history or uncontrolled neurological disorders or seizures. Participants with medically controlled active or chronic neurological diseases can be enrolled in the study as per investigator assessment, provided that their condition will allow them to comply with the requirements of the protocol (e.g. completion of the diary cards, attend regular phone calls/study site visits, perform self-swabbing (study participants in China only). EXC#5
- Significant underlying illness that in the opinion of the investigator would be expected to prevent completion of the study (e.g., life-threatening disease likely to limit survival to less than 1 year). EXC#6
- Serious or unstable chronic illness. EXC#7
- Any other clinical condition that, in the opinion of the investigator, might pose additional risk to the participant due to participation in the study. EXC#8

### 5.2.2. Prior/Concomitant Therapy

- Previous vaccination with RSV vaccine. EXC#9
- Use of any investigational or non-registered product (drug, vaccine or invasive medical device) other than the study intervention(s) during the period beginning 30 days before the dose of study intervention(s), or their planned use during the study period. EXC#10
- Planned or actual administration of a vaccine not foreseen by the study protocol in the period starting 30 days before and ending 30 days after study intervention administration, with the exception of COVID-19 and inactivated/subunit influenza vaccines which can be administered up to 14 days before or from 14 days after each study intervention. EXC#11

*Note: In case an emergency mass vaccination for an unforeseen public health threat (e.g.: a pandemic) is recommended and/or organized by the public health authorities, outside the routine immunization program, the time period described above can be reduced if necessary for that vaccine provided it is used according to the local governmental recommendations and that the Sponsor is notified accordingly.*

- Administration of long-acting immune-modifying drugs or planned administration at any time during the study period (e.g., infliximab). EXC#12
- Administration of immunoglobulins and/or any blood products or plasma derivatives during the period starting 90 days before the study intervention administration or planned administration during the study period. EXC#13
- Chronic administration (defined as more than 14 consecutive days in total) of immunosuppressants or other immune-modifying drugs during the period starting 90 days prior to the study intervention administration or planned administration during the study period. For corticosteroids, this will mean prednisone  $\geq 20$  mg/day, or equivalent. Inhaled and topical steroids are allowed. EXC#14

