## 2. INTRODUCTION

### 2.1. Study rationale

GlaxoSmithKline Biologicals SA (GSK) has developed a new respiratory syncytial virus (RSV) PreFusion protein 3 OA (RSVPreF3 OA) vaccine for the prevention of RSV-associated (subtypes A and B) lower respiratory tract disease (LRTD) disease in adults  $\geq 60$  years of age (YOA). The vaccine was first approved for use in adults  $\geq 60$  YOA in the United States (US) on 03 May 2023, under the trade name *Arexvy*. To date, the vaccine is also approved in the European Union, United Kingdom, Canada, Japan, Hongkong and Australia. The assessment in other countries is ongoing.

The purpose of the current study is to evaluate the immunogenicity of the investigational RSVPreF3 OA vaccine in older adults  $\geq 60$  YOA in China, in comparison with the immune response generated in overseas population since vaccine efficacy against LRTD has been demonstrated following a single dose of the RSVPreF3 OA vaccine in the global efficacy study RSV OA=ADJ-006. In addition, the safety, reactogenicity and occurrence of ARI (in study participants in China only) after administration of the vaccine will also be assessed as secondary objectives.

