## **6.9. Prior and concomitant therapy**

Any medication or vaccine (including over-the-counter or prescription medicines, recreational drugs, and/or herbal supplements) or other specific categories of interest that the participant is receiving at the time of enrollment or receives during the study must be recorded along with:

- Reason for use
- Dates of administration including start and end dates
- Dosage information including dose and frequency

The medical monitor should be contacted if there are any questions regarding concomitant or prior therapy.

At each study visit/contact, the investigator or delegate should question the participant about any medications/products taken and vaccinations received by the participant.

The following concomitant medication(s)/product(s)/vaccine(s) must be recorded in the eCRF:

- All concomitant medication, except vitamins and dietary supplements, administered during the 30-day period following the administration of study vaccine.
- All concomitant vaccination during the entire study period.
- All concomitant medication including vaccines/products which may explain/cause/be used to treat an SAE/pIMD as defined in Sections 8.4.1 and 8.4.3. These must also be recorded on the Expedited AE report.
- For all AF AESIs (including serious and non-serious), concomitant drugs which could be associated with development or worsening of AF must be reported in the AF follow-up questionnaire.
- Any antipyretic administered in the period starting 6 hours before vaccination and ending 12 hours after vaccination need to be recorded on the eCRF. An anti-pyretic is considered prophylactic when given in the absence of fever, to prevent fever from occurring.
- All concomitant medications taken for the treatment of an ARI (including prescribed drugs [e.g. antibiotics] and self-treatment) or for an ARI-related complication (Study participants in China only).
- All concomitant medications including vaccines/products leading to discontinuation of the study intervention or an elimination from the analysis (refer to Section 5.2.2 for details).

The Local Clinical Lead should be contacted if there are any questions regarding concomitant or prior therapy.

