ESTIMAND FOR SECONDARY IMMUNOGENICTY

The clinical question of interest is:

- to evaluate the humoral immune response after RSVPreF3 OA investigational vaccine administration in Chinese older adult with ≥ 60 YOA compared to RSV-OA overseas group, when vaccinated as per protocol, up to 6 months post-vaccination.
- to evaluate the humoral immune response after RSVPreF3 OA investigational vaccine administration in Chinese older adult with ≥ 60 YOA compared to RSV-OA immunogenicity subset of global efficacy study RSV OA=ADJ-006, when vaccinated as per protocol.

The estimand for secondary immunogenicity objectives are described in [Table 2](#):

Table 2 Study estimand - secondary immunogenicity objective

Attributes					
Treatment	Population	Endpoint (variable)	Intercurrent events (ICEs)		Population level summary
			Description	Handling strategy	
RSVPreF3 OA investigational vaccine at Day 1.	Chinese and Oversea OA with ≥60 YOA	
 RSV-A neutralizing titers at baseline, 1 month (Day 31) and 6 months after the RSVPreF3 OA investigational vaccine administration. RSV-A seroresponse at 1 month (Day 31) and 6 months after the RSVPreF3 OA investigational vaccine administration. RSV-B neutralizing titers at baseline, 1 month (Day 31) and 6 months after the RSVPreF3 OA investigational vaccine administration. RSV-B seroresponse at 1 month (Day 31) and 6 months after the RSVPreF3 OA investigational vaccine administration. 	Taking prohibited medication /vaccine or intercurrent medical condition prior to analysis timepoint.	Data collected after ICEs will be excluded from the analysis (Hypothetical strategy) Rationale: To evaluate the immunogenicity parameters in the absence of ICE.	GMTs with 95% CI for RSV-A and RSV-B neutralizing titers at baseline, 1 month (Day 31) and 6 month after RSVPreF3 OA investigational vaccine administration Seroresponse rate (SRR) with 95% CI for RSV-A and RSV-B neutralizing titers at 1 month (Day 31) and 6 months after RSVPreF3 OA investigational vaccine administration

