3.1.3. Elimination from Per-Protocol Set

A participant will be excluded from the populations for analysis under the following conditions:

- For codes 800, 900, 1030, 1060, 1070, 1080, 1090 and 2010: participants will be eliminated for all visits.
- For codes 1040, 2040 and 2050: participants will be eliminated from a specific visit (at which the condition is met) onwards.
- For codes 2020 2090, 2100, 2120: participants will be eliminated at the specific visit at which the condition is met.

Table 6 List of elimination codes

Code	Condition under which the code is used	Visit / Contact (timepoints) where the code is checked	Visit from when it is applicable	Applicable for analysis set/endpoint
800	Fraudulent data	All	All	Enrolled Set, ES, PPS
900	Invalid informed consent	All	All	Enrolled Set, ES, PPS
1030	Study intervention not administered at all	Visit 1	All	ES, PPS
1040	Administration of concomitant vaccine(s) forbidden in the protocol (as defined in Section 5.2.2 of protocol)	All	From the specific visit the condition is met	PPS
1060	Randomization code was broken (Chinese participants only)	All	All	PPS
1070	Vaccine administration not according to protocol: 
 • Participant was vaccinated with the correct vaccine but containing a lower volume • Wrong replacement or study vaccine administered (not compatible with the vaccine regimen associated to the treatment number) • Route of the study vaccine is not intramuscular • Wrong reconstitution of administered vaccine 	Visit 1	All	PPS
1080	
 • Vaccine administration after a temperature deviation • Vaccine administered despite a Good Manufacturing Practices (GMP) no-go temperature deviation 	Visit 1	All	PPS
1090	Vaccine administration after expiration	Visit 1	All	PPS
2010	Protocol deviation linked to inclusion/exclusion criteria	All	All	PPS
2020	All Pre-dose results are missing	Visit 1	At the specific visit the condition is met	PPS

Code	Condition under which the code is used	Visit / Contact (timepoints) where the code is checked	Visit from when it is applicable	Applicable for analysis set/endpoint
2040	Administration of any medication forbidden by the protocol (as defined in Section 5.2.2 of protocol)	All	From the specific visit the condition is met.	PPS

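### A locally registered RSV vaccine taken more than 30 days after the study dose is not a prohibited vaccine, so the descriptive Month 6 per-protocol comparison can retain boosted titres

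*Protocol*

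**What the plan says.** **Vaccines the protocol rules out (Section 5.2.2).**
- The RSV-specific criterion reads "Previous vaccination with RSV vaccine. EXC#9". It applies at entry.
- EXC#10 concerns "Use of any investigational or non-registered product (drug, vaccine or invasive medical device) other than the study intervention(s"), in the 30 days before the dose or where use during the study is planned.
- EXC#11 covers any other vaccine, planned or actual, "in the period starting 30 days before and ending 30 days after study intervention administration". COVID-19 and inactivated or subunit influenza vaccines have a 14-day spacing instead.

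**How the SAP uses that list.** In SAP Section 3.1.3, Table 6, code 1040 is triggered by "Administration of concomitant vaccine(s) forbidden in the protocol (as defined in Section 5.2.2 of protocol"). Its effect is stated as: "For codes 1040, 2040 and 2050: participants will be eliminated from a specific visit (at which the condition is met) onwards".

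**The estimand.** For secondary immunogenicity, SAP Table 2 gives the intercurrent event as "Taking prohibited medication /vaccine or intercurrent medical condition prior to analysis timepoint". Data after the event are excluded under a hypothetical strategy. The rationale in SAP Section 1.1 is to estimate the vaccine's effect free of the influence of other medications, vaccinations and medical conditions.

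**The analysis.** SAP Section 4.3.1.1 reports the Month 6 GMT ratio and SRR difference, Overseas against China, on the Per-Protocol Set, with a model like the primary one. SAP Section 4.3.1 calls these comparisons descriptive.

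**The data.** Protocol Section 6.9 requires recording of "All concomitant vaccination during the entire study period". SAP Section 6.1.5 tabulates only vaccinations in the first 30 days.

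**The concern.** Among vaccines, a second RSV vaccine is the most direct way to change an RSV neutralising titre. The Month 6 comparison describes how well the response persists in China relative to Overseas, and its estimand is meant to show titres undisturbed by other vaccinations. If the rule that implements the estimand stops looking 30 days after the dose, a participant boosted later counts as a per-protocol responder at Month 6. That inflates the titre and SRR of whichever group the participant belongs to. The planned vaccination table would not show it, because it also stops at 30 days.

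**Working it through.** **Step 1. Does any rule catch the event?** Take a participant who receives an RSV vaccine registered in their own country between 30 days after the study dose and the Month 6 sample.

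| Rule | Applies? |
|---|---|
| EXC#9 | No. It concerns vaccination before the study |
| EXC#10 | No. The product is registered locally |
| EXC#11 | No. The window has closed |
| Code 1040 | No. It draws on Section 5.2.2 |
| Code 2010 | No. It is for eligibility deviations |
| Code 2040 | No. It is for forbidden medication under Section 5.2.2 |
| Code 2050 | Possibly. It permits, but does not require, removal for a condition able to alter the immune response; it is titled as a medical condition and does not name vaccination |
| SAP Table 2 event | No, unless code 2050's reading is adopted. The vaccine is not prohibited |

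**Step 2. How much follow-up lies outside the window?** The Month 6 sample is due 180 to 210 days after the dose (Protocol Table 4). 180 − 30 = 150 and 210 − 30 = 180, so 150 to 180 days are uncovered. The Visit 2 sample is due at 30 to 42 days, which leaves at most 42 − 30 = 12 days uncovered before the Day 31 endpoint.

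**Step 3. Size.** The plan gives no figure for re-vaccination, for the size of a boost, or for Month 6 precision. Its stated inputs are 800 Overseas and 1200 RSV OA China participants, 10% attrition and an SD of 0.45 for log10 titres. After attrition that leaves 720 and 1080. With these, the Day 31 power table reproduces: Scenario 1 RSV-B SRR gives 90.5% by the score method (stated 90.5%), and a GMR of 1.19 gives 99.6% (stated 99.6%). They are therefore a fair basis for scale.

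Suppose a share f of the Overseas Month 6 Per-Protocol Set is re-vaccinated, each with a k-fold higher titre, independently of baseline titre and with China unaffected. The Overseas mean log10 titre rises by f × log10(k), so the GMT ratio is multiplied by k^f. Only participants who were not already seroresponders can add to the SRR, so it rises by at most f × (1 − Month 6 SRR). Both f and k are assumptions, as is the Month 6 SRR.

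| f | f × 720 | Ratio factor, k = 2 | Ratio factor, k = 4 | Maximum SRR rise in points, Month 6 SRR 70% / 50% / 30% |
|---|---|---|---|---|
| 1% | 7.2 | 1.007 | 1.014 | 0.3 / 0.5 / 0.7 |
| 2% | 14.4 | 1.014 | 1.028 | 0.6 / 1.0 / 1.4 |
| 5% | 36 | 1.035 | 1.072 | 1.5 / 2.5 / 3.5 |

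For comparison, the 95% CI half-width on the log10 scale is 1.96 × 0.45 × √(1/720 + 1/1080) = 0.0424, a factor of 1.103. At f = 2%, k = 2 the shift is 0.02 × 0.301 = 0.0060, about 14% of that half-width. The shift would equal the half-width only at f of about 14% (k = 2) or 7% (k = 4). Re-vaccination in the China group would move the ratio the other way by the same factor.

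**The case against.** The case against is strong on importance, and most of it stands.

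- **The event is unlikely.** The Overseas arm is open label and the regimen is a single dose, so those participants know they have just had an RSV vaccine. At f = 5%, 36 of 720 would have to take another within about six months.
- **No decision rests on Month 6.** All four hypotheses concern 1 month, and the SAP advises caution in reading the secondary comparisons.
- **Removal is not impossible.** A reader might infer that no elimination code could apply. The documents do not go that far. Code 2050 and the Per-Protocol Set's requirement of no interfering intercurrent conditions leave room for a judgement call. What they lack is a rule that must be applied.
- **The arm imbalance is not established.** A reader might conclude that the gap falls mainly on the Overseas group and so biases against China. Licensing points that way: "To date, the vaccine is also approved in the European Union, United Kingdom, Canada, Japan, Hongkong and Australia", besides the United States, while Protocol Section 4.2.2 says no RSV vaccine is licensed in China. But uptake is not given. The Republic of Korea, which has its own protocol appendix and SAP analysis, is not on the approval list. For use during the study, EXC#10 refers only to planned use, so unplanned use of an unregistered vaccine in China may escape it too. Greater Overseas exposure is an inference that varies by country.
- **The RSV illness description is not affected.** A reader might extend the point to the ARI surveillance in China. That analysis uses the Exposed Set under a treatment-policy strategy, so per-protocol elimination plays no part and keeping such cases is what the plan intends.

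The rule chain itself survives: the cut-off classifies a later RSV vaccine as permitted, which the stated rationale of the estimand does not support.

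**Conclusion.** This holds as a minor point. The 30-day limit in EXC#11, carried into code 1040 and SAP Table 2, leaves a later, locally registered RSV vaccine outside both the elimination rule and the intercurrent-event definition. The affected results are the descriptive Month 6 GMT ratio and SRR difference. The likely shift is small: a factor of 1.007 to 1.014 for 1% to 2% re-vaccinated with a two-fold rise, against a CI half-width of 1.103. These sizes rest on assumed values of f and k, the planned numbers after 10% attrition, and the Day 31 SD carried over to Month 6.

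A reader might also infer a threat to the co-primary bridging conclusion. The documents do not support that: at most 12 days before the Visit 2 sample are uncovered, and the Day 31 power figures do not change. The reason to act is that the correction is nearly free and settles the classification before Month 6 titres are examined.

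**What to change.** Two changes to the SAP, both analysis rules that place no restriction on care:

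1. In Table 6, extend code 1040 so that receipt of any non-study RSV vaccine after Visit 1 and before a blood sample eliminates the participant from the Per-Protocol Set from that visit onwards, in all groups.
2. In Table 2, name the same event as an intercurrent event, handled by the hypothetical strategy already chosen.

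Stating the number of such participants by group and visit would be a useful addition, since the planned vaccination table ends at 30 days.

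The cost is a few lines of text and the loss of a few Month 6 per-protocol participants. No new data collection is needed, because Section 6.9 of the protocol already requires the vaccinations to be recorded. Those removed who have serology would count towards the 5% exclusion threshold that triggers the complementary Exposed Set analysis. If nobody was re-vaccinated, no result changes.
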